8.2.3.2 Radiological response

In the per protocol population:

The best overall response will be presented in contingency table with numbers and percentages. The objective response (CR/PR) and complete response rates will be reported with exact (binomial) 95% confidence interval. The medians of objective (PR/CR) and complete (CR) response duration will be extracted from their respective Kaplan-Meier curves. The Reflected Method will provide 95% confidence interval.

8.2.3.3 Overall Survival

In the per protocol population:

OS will be compared between trabectedin and control arm. A Cox regression model including treatment and stratification factors at randomization (except institution) will be fit. If for a factor, Proportional Hazards assumptions (PH) are not respected (assessed by Schoenfeld residuals), the model will be stratified (i.e. not adjusted) by this factor. The superiority of trabectedin against the control arm will be tested at 5% two-sided significance level. The treatment HR estimate will be presented with 95% CI. The OS probability at 6 months (OS6), at 1 year (OS12) and the median OS (mOS) will be extracted from the Kaplan-Meyer OS curve. 95% confidence intervals will be computed based on the Greenwood's formula. For the median the Reflected Method will provide 95% confidence intervals.

8.2.3.4 Safety and tolerability

In the safety population at baseline and during treatment and follow-up:

The safety and tolerability analyses will be presented at baseline and for the whole study duration. Severe grades which did not resolve after treatment discontinuation or emerged during follow-up will be identified and listed. All forms up to the last safety assessment before progression or start of further antitumoral therapy will be used. Baseline will include all information recorded up to the nearest date prior to or at randomization. Exceptionally, assessments performed after randomization but before start of protocol treatment can be considered. There will be no formal comparison of safety endpoints. No p-value and confidence intervals will be carried out. Baseline laboratory and AE grades will not be accounted for in whole study duration safety analyses. Laboratory and AE events occurring in patients who did not start their allocated treatment will be reported separately.

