6.3 During treatment

The following need to be performed on day 1 of each treatment cycle or within 72 hours before:

- ◆ Clinical examination (WHO PS, blood pressure, pulse rate, body weight, and body temperature).
- ◆ Assessment of all adverse events that have occurred since the previous visit and ongoing events from previous cycles should be followed.
- ◆ Complete blood counts to include hemoglobin, white blood cells, neutrophils, lymphocytes, platelets. For the experimental arm only, additional monitoring of hematological values should occur weekly during the first two cycles of therapy, and at least once between treatments in subsequent cycles
- ◆ A serum chemistry assessment to include at least creatinine, total bilirubin, ALT, AST, ALP, CPK, albumin, LDH, sodium, potassium, glucose, calcium. For the experimental arm only, additional monitoring of serum chemistry values should occur weekly during the first two cycles of therapy, and at least once between treatments in subsequent cycles
 - ◆ If ALP > 2.5 ULN, ALP hepatic isoenzyme 5-nucleotidase and/or GGT tests must be performed; ALP hepatic isoenzyme or 5-nucleotidase and/or GGT must be within the normal range.
 - ◆ Creatinine clearance will be calculated by Cockcroft and Gault formula (see Appendix E)
 - ◆ For the serum chemistry parameters not collected on the Serum Chemistry form: in case of abnormal value please record it as adverse event on the Adverse Event forms (grade, relationship, seriousness).
- ◆ Cranial MRI every 9 weeks from randomization and if clinically indicated
- ◆ Recording of corticosteroid dose every 9 weeks
- ◆ CT thorax/abdomen only if clinically indicated; if tumorous or unclear lesions detected repeat CT every 9 weeks and if clinically indicated
- ◆ HRQoL: QLQ-C30 (v3) and the BN-20 questionnaire: regardless the treatment arm, at week 3, week 6 and week 12 after treatment start (for more information see chapter 10).
- ◆ Pregnancy test (every two cycles)

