6.4 After the end of treatment (Follow-up)

6.4.1 30 days after last administration of study drug

- ◆ Clinical examination (WHO performance status, blood pressure, pulse rate, body weight and body temperature)
- ◆ All ongoing adverse events from previous cycles should be followed until their resolution or stabilization or until the start of new anticancer therapy.
- ◆ Pregnancy test
- ◆ Complete blood counts to include hemoglobin, white blood cells, neutrophils, lymphocytes, platelets.
- ◆ A serum chemistry assessment to include at least creatinine, total bilirubin, ALT, AST, ALP, GGT, CPK, albumin, LDH, sodium, potassium, glucose, calcium.
 - ◆ If alkaline phosphatase > 2.5 ULN, hepatic isoenzymes 5-nucleotidase or GGT determinations must be performed; hepatic isoenzymes 5-nucleotidase and/or GGT must be within the normal range.
 - ◆ Creatinine clearance will be calculated by Cockcroft and Gault formula (see Appendix E)
 - ◆ Only the following parameters will be collected on the serum biochemistry form: creatinine, total bilirubin, ALT, AST, ALP hepatic isoenzymes 5-nucleotidase (if applicable), GGT (if applicable), CPK.
 - ◆ For the serum chemistry parameters not collected on the Serum Chemistry form: in case of abnormal value please record it as adverse event on the Adverse Event forms (grade, relationship, seriousness).

6.4.2 3 months after last administration of study drug

- ◆ Pregnancy test

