7.1.2 Tumor response evaluation

All patients will have their overall response (OR) from the start of study treatment until the end of treatment classified as outlined below:

Complete Response (CR): disappearance of all *target* and *non-target* lesions. Residual lesions (other than nodes < 10 mm) thought to be non-malignant should be further investigated (by cytology or PET scans) before CR can be accepted. Clinical evaluation must be stable or improving. No steroids should be needed.

Partial Response (PR): at least a 50% decrease in the sum of the product of perpendicular diameters of the target lesions, as compared to baseline. Non target lesions must be non-PD. Clinical evaluation must be stable or improving. Steroid dose must be stable or diminishing.

Stable Disease (SD): Neither sufficient shrinkage to qualify for PR nor sufficient increase to qualify for PD taking as reference the smallest tumor measurement recorded during the study. Clinical evaluation must be stable or improving. Steroid dose must be stable or diminishing.

Progressive Disease (PD): at least a 25% increase in the sum of products of perpendicular diameters of the measured lesions taking as references the smallest tumor measurement recorded during the study (including the baseline scan). Appearance of new lesions (including extracranial) will also constitute PD (including lesions in previously unassessed areas). In exceptional circumstances, unequivocal progression of non-target disease may be accepted as evidence of disease progression, where the overall tumor burden has increased sufficiently to merit discontinuation of treatment, for example where the tumor burden appears to have increased by at least 73% in volume (which is the increase in volume when all dimensions of a single lesion increase by 20%). Modest increases in the size of one or more non-target lesions are NOT considered unequivocal progression. If the evidence of PD is equivocal (target or non-target), treatment may continue until the next assessment, but on further documentation, the earlier date must be used. Worsening of the clinical evaluation should also be recorded as PD.

Table 1: Macdonald response criteria

	CR	PR	SD	PD
T1-Gd+	0	decrease \geq 50%	decrease $<$ 50% or increase $<$ 25%	increase \geq 25%
New Lesion	no	No	no	Yes*
Steroids	no	stable or decreasing	stable or decreasing	NA
Clinical evaluation	stable or improving	stable or improving	stable or improving	worsening
	All	All	All	Any

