7.2 Evaluation of safety

7.2.1 Adverse events

All adverse events will be recorded; the investigator will assess whether those events are drug related (reasonable possibility, no reasonable possibility) and this assessment will be recorded in the database for all adverse events.

Only the worst grade per CTCAE category will be recorded per cycle. The collection period will start from randomization up to 30 days after administration of the last dose of protocol treatment or until the start of a new antitumor therapy, whichever occurs first.

All adverse events must be followed until resolution or stabilization.

Whenever possible, the Investigator will record the main diagnosis instead of the signs and symptoms normally included in the diagnoses.

Investigators must pursue and obtain information adequate both to determine the outcome and to assess whether it meets the criteria for classification as a SAE requiring immediate notification.

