15.6 Reporting procedure for investigators

This procedure applies to all Serious Adverse Events (SAEs) occurring from the time a subject is randomized until 30 days after last protocol treatment administration, or until the start of a new antitumor therapy, whichever occurs first; and to any SAE that occurs outside of the SAE detection period (after the 30-days period), if it is considered to have a reasonable possibility to be related to the protocol treatment or study participation.

Randomization till 30 days after last protocol treatment administration, or until the start of a new antitumor therapy, whichever occurs first:	All SAEs
From day 31 after last protocol treatment administration (or after start the start of a new antitumor therapy):	Only related SAEs

Any secondary malignancy should also be reported in expedited way on a SAE form with the appropriate seriousness criteria!

All reporting must be done by the principal investigator or authorized staff member (i.e. on the signature list) to confirm the accuracy of the report.

All SAE data must be collected on the study-specific SAE form.

All SAEs must be reported immediately and no later than 24 hours from the time the investigator or staff became aware of the event.

All SAE-related information needs to be provided in English.

All additional documents in local language must be accompanied by a translation in English, or the relevant information must be summarized in a follow-up SAE report form.

All SAE-related information must be send to the EORTC Pharmacovigilance Unit:

EORTC Pharmacovigilance Unit:

[contact]

[contact]

To enable the Sponsor to comply with regulatory reporting requirements, all initial SAE reports should always include the following minimal information: an identifiable patient (SeqID), a suspect medicinal product if applicable, an identifiable reporting source, the description of the medical event and seriousness criteria, as well as the causality assessment by the investigator. Complete information requested on the SAE form of any reported serious adverse event must be returned within 7 calendar days of the initial report. If the completed form is not received within this deadline, the Pharmacovigilance Unit will make a written request to the investigator.

Queries sent out by the EORTC Pharmacovigilance Unit need to be answered within 7 calendar days.

The investigator must provide any relevant information as requested by the Sponsor in addition to that on the CRF.

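### Section 8.2.3.4 ends the safety tables at the last assessment before progression, although adverse events and laboratory values are collected to 30 days after the last dose whether or not the patient has progressed, so collected toxicity can be left out.

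*Combined protocol and SAP*

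**What the plan says.** **Analysis.** Section 8.2.3.4 sets the scope broadly: "The safety and tolerability analyses will be presented at baseline and for the whole study duration". It then limits the data: "All forms up to the last safety assessment before progression or start of further antitumoral therapy will be used". One further provision reaches past treatment: "Severe grades which did not resolve after treatment discontinuation or emerged during follow-up will be identified and listed". Section 8.2.3.4.4 builds the SAE tables after reconciliation with the pharmacovigilance listing and gives no cut-off of its own.

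**Collection.** Section 7.2.1: "The collection period will start from randomization up to 30 days after administration of the last dose of protocol treatment", or to the start of a new antitumor therapy if that is earlier. Section 15.6 sets the same period for all SAEs: "Randomization till 30 days after last protocol treatment administration, or until the start of a new antitumor therapy, whichever occurs first". It also collects related SAEs after that. Section 6.4.1 schedules blood counts and serum chemistry 30 days after the last dose and adds: "All ongoing adverse events from previous cycles should be followed until their resolution or stabilization or until the start of new anticancer therapy". The summary table in 6.5 marks adverse events, hematology and chemistry at the same visit. None of these provisions stops at progression.

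**Progression.** Under 5.5 progression ends treatment. For equivocal progression, 7.1.2 says that "treatment may continue until the next assessment, but on further documentation, the earlier date must be used".

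**The concern.** The new-therapy half of the analysis cut agrees with the collection period. The progression half does not, and it can remove data by two routes.

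1. *Stopping for progression.* On-treatment adverse event visits take place at the start of a cycle and look back over the time since the previous visit (6.3). When a scan shows progression and treatment stops, toxicity of the last cycle may first be reported at or after progression, which is past the cut.
2. *Back-dated progression.* If treatment continues after an equivocal scan and progression is later confirmed, the earlier date applies. Forms completed during the continued dosing then lie after progression, although the patient was on study drug.

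Safety is a secondary endpoint, and these descriptive tables are how it is reported. What can go missing is chiefly non-serious grade 1-2 events, severe final-cycle events that resolve, and laboratory values from the 30-day visit.

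**Working it through.** The plan states no figure for this point, so there is none to reproduce. The windows come first, then a day count for scale.

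| Item | Ends at | Stops at progression? |
|---|---|---|
| AE collection (7.2.1) | last dose + 30 days, or new therapy | no |
| SAE collection (15.6) | the same; related SAEs also later | no |
| Laboratory visit (6.4.1, 6.5) | 30 days after last dose | no |
| Safety tables (8.2.3.4) | last safety assessment before progression, or new therapy | **yes** |

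**Inputs for the day count.** Cranial MRI every 63 days from randomization (6.3). Treatment starts d = 0 to 21 days after randomization (section 6). Cycles last 21 days for trabectedin and 21 or 28 days for control (section 6). AE visits fall on the dosing day or up to 72 hours (3 days) before it (6.3). The collection window ends 30 days after the last dose.

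**Assumptions.** Forms are dated by visit, dosing is on time, progression is found at a scheduled scan, and no new therapy starts within 30 days. Randomization is day 0.

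**Measure.** Gap = (last dose day + 30) − (day of the last usable AE form).

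*3-week cycles, d = 0, progression on the day-63 scan.* Doses fall on days 0, 21 and 42, and the window ends on day 42 + 30 = 72.
- Visit on day 63, counted as before progression: 72 − 63 = **9** days.
- Visit on day 60: 72 − 60 = 12 days.
- Day-63 form not counted, last form on dosing day 42: 72 − 42 = 30 days.
- As above, but that visit was held 72 hours before dosing, on day 39: 72 − 39 = **33** days.

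For d = 4 to 20 the next pre-dose visit always falls after the scan, so the gap is 30 to 33 days. For example, with d = 4 the last dose is on day 46, the next dose is due on day 67 and its visit is on day 64 at the earliest. The range over all d is 9 to 33.

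*4-week cycles, d = 7.* Doses fall on days 7 and 35, the next is due on day 63, and the window ends on day 35 + 30 = 65.
- Visit on day 63: 65 − 63 = **2** days.
- Last form 72 hours before the last dose, on day 32: 65 − 32 = **33** days.

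*Back-dated progression, 3-week cycles, d = 0.* The scan on day 63 is equivocal, doses continue on days 63, 84 and 105, and progression is confirmed on day 126 and dated to day 63. The window ends on day 105 + 30 = 135.
- Last usable form on day 63: 135 − 63 = **72** days.
- On day 42: 135 − 42 = 93 days.
- On day 39: 135 − 39 = **96** days.

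Three doses follow the progression date. Three is an upper bound: an earlier, clinically indicated MRI or a dose delay would reduce it.

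**What the existing safeguards recover.** The 8.2.3.4 listing covers only severe grades that persist or emerge in follow-up, and a listing does not enter frequencies or percentages. The reconciliation in 8.2.3.4.4 may bring back SAEs, but the section does not say whether SAEs after progression count. Nothing comparable covers the all-AE, related-AE or laboratory tables.

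**The case against.** **The sentence may be meant more mildly.** Section 8.2.3.4 speaks of treatment and follow-up and of the whole study, and the sentence could be a loose statement of how far follow-up forms count. That is possible, but the text names progression as the limit and offers no exception. This is why the point is put as what can happen if the rule is followed as written.

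**Form dating is not in the protocol.** Section 7.2.1 records the worst grade per cycle, and 14.1 leaves the form schedule to separate guidelines. If a final-cycle form counts as belonging to a cycle begun before progression, the first route shrinks or closes. This stands. It limits how firmly the loss can be asserted, and it also means the plan itself does not secure the data.

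**A pre-progression cut has a rationale.** Clinical worsening counts as progression (7.1.2), and 15.2 generally keeps progression events out of SAE reporting, so the cut limits mixing of disease symptoms with toxicity. This also stands. It supports keeping that cut as a second presentation, but not as the only one.

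**Stronger readings that the documents do not support.** A reader might infer that most patients lose a month of safety data, because the design PFS-6 values imply that 1 − 0.35 = 65% (trabectedin) and 1 − 0.15 = 85% (control) have progressed or died by 6 months. Those figures mix progression with death, and the documents give no rate of equivocal progression, so no share of patients follows. A reader might also infer that reported frequencies will be too low. A table cell changes only if an excluded form brings a new term or a higher grade, and that is not shown. Finally, a reader might infer a difference between arms that the fix would cure. Section 6.3 says "For the experimental arm only, additional monitoring of hematological values should occur weekly during the first two cycles of therapy", with at least one interim sample per later cycle. Laboratory ascertainment is therefore unequal between arms under any cut-off, and the fix does not remove this.

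**Conclusion.** The mismatch between the collection window and the analysis cut is real and textual. Followed as written, 8.2.3.4 can exclude collected final-cycle and post-dose toxicity in patients who stop for progression and, where progression is back-dated, toxicity from doses given after the recorded progression date. The safeguards close only part of the gap.

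The scale is illustrative: 9 to 33 days on 3-week cycles, 2 to 33 on 4-week cycles, and 72 to 96 days with up to three doses after back-dating by a full 9-week interval. It rests on visit-dated forms, on-time dosing, scheduled scans and no new therapy within 30 days. How many patients or table cells are affected cannot be stated from the documents. The effect is confined to descriptive safety reporting; efficacy, alpha and power do not change. The point should be settled before the safety tables are produced.

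**What to change.** In 8.2.3.4, replace the sentence on which forms are used with wording such as: *Safety tables use all forms from randomization, in patients who started treatment and with baseline handled as stated, to 30 days after the last dose, irrespective of progression or of a back-dated progression date, and end at the start of new antitumor therapy. Forms from later follow-up before progression are retained as now provided.*

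The last clause keeps the 9-weekly follow-up of ongoing events under 6.4.3. In patients who stop without progression the tables can therefore still run past 30 days, as they can now.

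In 8.2.3.4.4, state that the SAE tables use the same cut-off, and show later related SAEs separately. Keep the pre-progression cut as a supplementary presentation of the all-AE and related-AE tables only.

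**Cost.** A reworded rule in 8.2.3.4, one sentence in 8.2.3.4.4, one small table of later related SAEs and four supplementary tables (all AEs and related AEs, each for all grades and for grade 3/4). The data are already collected. The downside is that some progression symptoms will enter the all-AE tables. The related-AE and supplementary tables help to separate them, although relatedness is judged open-label.

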2.2 End-points

Primary end-point:

- ◆ Progression Free Survival (PFS)

Secondary end-points:

- ◆ Progression Free Survival at 6 months (PFS-6), median PFS (mPFS)
- ◆ Best overall response (BOR). Objective response (CR/PR), rate and median duration. Complete response (CR), rate and median duration.
- ◆ Overall survival (OS), OS probability at 6 (OS6) and 12 months (OS12), median OS (mOS)
- ◆ Safety (CTCAE v.4.0)
- ◆ Health-related Quality of life (QoL)

3 Patient selection criteria

- ◆ Age 18 or older
- ◆ Histological diagnosis of WHO grade II (chordoid meningioma, clear cell meningioma, atypical meningioma) or WHO grade III (papillary meningioma, rhabdoid meningioma, anaplastic/malignant meningioma) according to WHO 2007 classification.
- ◆ Radiologically documented progression of any existing tumor (growth > 25% in the last year) or appearance of new lesions (including intra- and extracranial manifestations)
- ◆ No more option for local therapy (resection or radiotherapy) after maximal feasible surgery and radiotherapy
- ◆ No prior systemic anti-neoplastic therapy for meningioma (patient may have received prior radionuclide therapy)
- ◆ Measurable disease (10 x10 mm) on cranial MRI no more than 2 weeks prior to randomization.
- ◆ WHO performance status 0-2
- ◆ Adequate liver, renal and hematological function within 4 weeks prior to randomization, defined as:
 - ◆ Neutrophils $\geq 1.5 \times 10^9/L$, hemoglobin $\geq 9 \text{ g/dL}$ or hemoglobin $\geq 5.6 \text{ mmol/L}$, platelets $\geq 100 \times 10^9/L$
 - ◆ Total Bilirubin $\leq 1 \times \text{ULN}$, SGPT/ALT and SGOT/AST $\leq 2.5 \times \text{ULN}$
 - ◆ Alkaline phosphatase $\leq 2.5 \times \text{ULN}$; if alkaline phosphatase $> 2.5 \text{ ULN}$, ALP hepatic isoenzyme and/or 5-nucleotidase and/or gamma glutamyltransferase (GGT) must be within the normal range
 - ◆ Albumin $\geq 30 \text{ g/L}$
 - ◆ Serum creatinine $\leq 1.5 \times \text{ULN}$
 - ◆ Creatinine clearance $> 30 \text{ ml/min}$ as calculated by Cockcroft and Gault formula (see Appendix E)
 - ◆ Creatine phosphokinase (CPK) $\leq 2.5 \times \text{ULN}$
- ◆ Normal cardiac function (LVEF assessed by MUGA or ECHO within normal range of the institution), normal 12 lead ECG (without clinically significant abnormalities). The following unstable cardiac conditions are not allowed:
 - ◆ Congestive heart failure

- ◆ Angina pectoris
- ◆ Myocardial infarction within 1 year before registration/randomization

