5.7.1.2 Permitted medications

- ◆ The use of growth factors is permitted

6 Clinical evaluation, laboratory tests and follow-up

The schedule of evaluation as described below applies to both treatment arms. A treatment cycle is defined as 3 weeks in the experimental arm and 3 or 4 weeks in the control arm, whatever is more appropriate for the selected treatment. Disease evaluation (MRI and/or CT) should follow exactly the schedule described below, irrespective of the treatment arm.

Treatment should start within an acceptable delay from randomization. A maximum delay of 21 days is accepted.

6.1 Within 4 weeks prior to randomization and within 4 weeks prior to treatment start

All evaluations performed more than 28 days prior to treatment start must be repeated.

- ◆ Informed consent
- ◆ Medical history and demographics (age, gender, medical conditions at entry)
- ◆ Clinical examination (including WHO performance status, neurological examination, blood pressure, pulse rate, body weight, height and body temperature)
- ◆ Recording of corticosteroid dose
- ◆ Assessment of all adverse events
- ◆ Cardiac monitoring: 12-lead ECG, LVEF (MUGA or echo)
- ◆ Complete blood counts will be performed, to include hemoglobin, white blood cells, neutrophils, lymphocytes, platelets.
- ◆ A serum chemistry assessment to include at least creatinine, total bilirubin, ALT, AST, alkaline phosphatase (ALP), CPK, albumin, LDH, sodium, potassium, glucose, calcium, hepatic isoenzymes 5-nucleotidase (if applicable), GGT (if applicable).
 - ◆ Alkaline phosphatase $\leq 2.5 \times$ ULN; if alkaline phosphatase $> 2.5 \times$ ULN, ALP hepatic isoenzyme and/or 5-nucleotidase and/or gamma glutamyltransferase (GGT) must be within the normal range. Creatinine clearance will be calculated by Cockcroft and Gault formula (see Appendix E)
 - ◆ For the serum chemistry parameters not collected on the Serum Chemistry form: in case of abnormal value please record it as adverse event on the Adverse Event forms (grade, relationship, seriousness).
- ◆ A serum pregnancy test is required in women of reproductive potential within 72 hours prior to randomization (and also within 72 hours prior to treatment start). The pregnancy test is to be repeated during protocol treatment every two treatment cycles.
- ◆ HRQoL: QLQ-C30 (v3) and the BN-20 questionnaire (for more information see chapter 10).

6.2 Within 2 weeks prior to randomization and within 4 weeks prior to treatment start

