8.2.3.4.1 Hematological parameters

The worst value of each hematological category will be identified and graded for each patient. Frequencies and percentages of each category will be tabulated per arm. A table with grade 3/4 frequencies and percentages will be provided.

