8.2.3.4.2 Biochemical parameters

The worst value of each biochemical category will be identified and graded for each patient. Frequencies and percentages of each category will be tabulated. A table with grade 3/4 frequencies and percentages will be provided.

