8.2.3.4.3 All AEs

The worst grade of each AE item will be identified for each patient. Frequencies and percentages of each CTCAE term will be tabulated grouped by SOC. Tables with all grades and grade 3/4 frequencies and percentages will be provided.

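### The whole-study safety tables ignore baseline grades, so laboratory abnormalities allowed at entry and unchanged are shown as on-study grades, and no table shows who worsened

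*Combined protocol and SAP*

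**What the plan says.** Section 8.2.3.4 sets out two displays: "The safety and tolerability analyses will be presented at baseline and for the whole study duration". It defines baseline as information up to randomization and, exceptionally, assessments after randomization but before treatment start. For the second display it adds: "Baseline laboratory and AE grades will not be accounted for in whole study duration safety analyses". It rules out testing: "There will be no formal comparison of safety endpoints".

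The subsections give the summary rules:

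- Hematology (8.2.3.4.1): "The worst value of each hematological category will be identified and graded for each patient".
- Biochemistry (8.2.3.4.2): "The worst value of each biochemical category will be identified and graded for each patient".
- All AEs (8.2.3.4.3): "The worst grade of each AE item will be identified for each patient".
- SAEs and related AEs (8.2.3.4.4 and 8.2.3.4.5) follow the same worst-grade pattern.

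Each subsection also plans a grade 3/4 table. None defines a treatment-emergent event, a worsening from baseline, or a shift table.

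Baseline data are collected. Section 6.1 requires hematology, serum chemistry and "Assessment of all adverse events" before randomization, and the summary table in 6.5 marks all three as mandatory.

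**The concern.** A worst-grade table is usually read as what happened to patients on treatment. Here it mixes what happened on treatment with what patients brought into the trial. The baseline table shows how many patients in each arm had a given grade at entry, but it is not linked patient by patient to the on-study grade. A reader therefore cannot tell an arm in which many patients worsened from one in which many patients entered with the abnormality.

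Safety is a named secondary endpoint (2.2). Because no formal comparison is planned, the descriptive tables are all the safety evidence the trial will report, and they need to be interpretable as they stand.

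**Working it through.** The plan states no figure on this point, so there is none to reproduce. The check has three parts.

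**1. Laboratory values: does an unchanged entry abnormality reach the on-study table?**

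- Section 3 admits hemoglobin from 9 g/dL, and ALT/AST, ALP and CPK up to 2.5 x ULN. It sets no limit for lymphocytes, LDH, sodium, potassium, glucose or calcium.
- Section 6.3 repeats hematology and chemistry on day 1 of each cycle or within 72 hours before.
- The day 1 criteria in 5.6.1.2 accept the same hemoglobin, ALT/AST, ALP and CPK limits, so an unchanged value does not hold up the next cycle and is measured again.
- Sections 8.2.3.4.1 and 8.2.3.4.2 grade the worst value, and nothing subtracts baseline.

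So it does. This holds even on the narrowest reading of the sentence, in which baseline records are only left out of the search for the worst value, because the repeat measurement is an on-study record.

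**2. AE forms: the same question**

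- Pointing towards inclusion: 6.1 has AEs assessed at baseline, 6.3 has ongoing events followed, and 7.2.1 has all AEs recorded. Sections 6.1 and 6.3 also ask that abnormal chemistry values not held on the Serum Chemistry form be entered as AEs, with no condition on change from baseline.
- Pointing away: 7.2.1 starts AE collection at randomization, 6.3 speaks of events since the previous visit and from previous cycles, and 15.1 asks for illnesses that begin on study or pre-existing ones that get worse.

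The documents do not settle this. The answer depends on whether sites enter unchanged pre-existing items on the on-study forms.

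**3. Size**

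Let *b* be the share with the item at entry, unchanged, and *r* the share of the remaining patients who develop it. Both are assumptions.

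- Planned table: displayed rate = *b* + (1 − *b*)*r*
- New events over all patients: (1 − *b*)*r*

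With *r* = 30% (trabectedin) and 10% (control):

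| *b* | Planned table | Ratio | New events, all patients | Ratio | Difference in each |
|---|---|---|---|---|---|
| 10% | 37% vs 19% | 1.95 | 27% vs 9% | 3.0 | 18 points |
| 20% | 44% vs 28% | 1.57 | 24% vs 8% | 3.0 | 16 points |
| 40% | 58% vs 46% | 1.26 | 18% vs 6% | 3.0 | 12 points |

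At *b* = 40%, unchanged entry findings make up 0.40/0.58 = 69% of the trabectedin figure and 0.40/0.46 = 87% of the control figure.

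Chance imbalance in *b* has SD = √[*b*(1 − *b*)(1/57 + 1/29)]. This gives 9.1 points at *b* = 20%, 10.5 at 30%, 11.2 at 40% and 11.4 at 50%. The displayed rate equals *r* + *b*(1 − *r*), so a shift in *b* enters it with weight 1 − *r*, here 0.7 or 0.9. In the new-event rate the weight is only *r* in size, 0.3 or 0.1. The sizes 57 and 29 are the per protocol targets in 8.1.1. The safety population also includes ineligible patients who started treatment, so it may be slightly larger.

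**The case against.** The strongest reply is that the rule is disclosed, is the same in both arms and feeds only descriptive tables. The sentence may simply keep the two displays apart, so that an abnormality seen only at baseline is not counted on study. A chance imbalance at entry would be visible in the baseline table, and related AEs are tabulated separately.

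Most of this stands and limits the point. It does not remove it:

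- The narrow reading still counts an unchanged laboratory value (part 1 of the check).
- The baseline table shows an imbalance in totals but not who worsened.
- The related-AE table rests on investigator attribution in an open-label trial, and the laboratory tables have no causality filter.

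Four stronger readings are tempting, and the documents do not support them:

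- A reader might infer that a 20-point difference shrinks to 12. The 20 points apply only to patients without the item at entry. Over all patients the new-event difference is also 12 points. If patients with the item at entry also worsened at those rates, they would no longer be unchanged, and their worsening would show as a higher worst grade.
- A reader might infer that unchanged tumor symptoms are certainly counted. Sections 7.2.1 and 15.1 leave that open.
- A reader might infer that the grade 3/4 tables are distorted throughout. Entry requires neutrophils of at least 1.5 and platelets of at least 100 x 10⁹/L, far from the 0.5 and 25 in 5.6.1.1, and bilirubin no higher than ULN. Grade 3/4 tables for parameters with entry limits should be largely unaffected.
- A reader might infer that toxicity weighs equally with activity in the decision to go on. Section 2.1 frames that question on antitumor activity, and the plan has no toxicity decision rule.

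**Conclusion.** The point holds as a modest improvement to descriptive safety reporting. For laboratory parameters it follows directly from 8.2.3.4 and the entry criteria. For symptoms, and for chemistry values recorded as AEs, it is conditional on form completion. The effect falls mainly on all-grade tables and on parameters without an entry limit: absolute rates are too high in both arms, the ratio between arms is pulled towards 1, and chance imbalance at entry is carried into the display.

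The percentages rest on assumed values of *b* and *r*. A prevalence of 40% is an illustration and cannot apply to bilirubin, for example. The rule is not an internal contradiction, does not favor one arm by design and has no bearing on the PFS analysis.

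**What to change.** Replace the sentence in 8.2.3.4 with wording to this effect:

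- The worst-grade tables are presented as planned.
- In addition, for each hematology parameter, and for each chemistry parameter whose values are captured on the laboratory forms, a shift table per arm shows baseline grade against worst on-study grade, with a row for missing baseline.
- AE tables also report, per arm, items absent at baseline or with a worst on-study grade above the patient's baseline grade.

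The limit to captured parameters is needed. The form list in 6.4.1 omits LDH, sodium, potassium, glucose, calcium and albumin, and 6.1 and 6.3 have parameters outside the form recorded as AEs only when abnormal. Shift tables cannot be promised for those. One line stating whether unchanged pre-existing items are entered on on-study AE forms would settle the conditional part.

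The cost is a wording change and a few extra descriptive tables. No new visits, tests or patients are needed.
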